13.10 Analysis of Exploratory Immune Endpoints

Will be done at the [name] Lab at UCSF and DFCI Center for Molecular Oncology Core.

We hypothesize that the number of CD8+ and CD4+ T cells will significantly increase following anti-PD-1 antibody treatment. IHC will be performed on bone metastasis biopsies obtained at baseline and on treatment to quantify tumor infiltration by CD8+ T cells, Tregs (FoxP3+ CD4+ cells), and total CD4 T cells (in both normal and tumor tissue).

We hypothesize that the treatment with Radium-223 will prime T cells and therefore lead to changes in the circulating T cell repertoire. We will assess this by performing TCR sequencing of circulating blood on baseline and on treatment blood samples. For each arm, the change in circulating TCR between pre-treatment and post- treatment will be assessed by calculating the number of unique clonotypes comprising the top 25th percentile of cumulative reads after sorting by clone abundance. Repertoire change between sequencing experiments will be measured using Morisita's distance.

To detect circulating antibodies in sera derived from the pretreatment and on therapytimepoints, spotted antigen arrays will be used. After standard preprocessing of the protein array data, Cluster and Treeview software will be used for unsupervised clustering of the data with Pearson correlation and complete linkage. For each array, an antigen is identified as being detected if its value is above the median. To determine the number of up- and down modulated antibodies, the difference in log2 intensity values of pretreatment and post-treatment samples will be taken for each patient to identify antigens that are detected differentially due to treatment. Number of antibodies with at least 2- or 4-fold difference between pretreatment and post-treatment samples will be compared between the treatment arms by performing two-sided Wilcoxon rank sum test.

Tumor tissue from each patient's biopsy will be evaluated by IHC for PD-L1 levels prior to administration of the drug. Two independent pathologists who are blinded to the patients' clinical outcomes (e.g., response, survival) will score the percentage of tumor cells exhibiting cell-surface staining for PD-L1. PD-L1 positivity is defined per core by a 5% expression threshold.^{54,55} Other levels of PD-L1 positivity will be explored. Patients with multiple cores will be considered PD-L1–positive if any specimen meets this criterion. Similarly, tumor will be stained for other immune checkpoints such as TIM-3, LAG-3, and PD-L2.

The bone metastasis biopsies will be evaluated to assess whether increased levels of MDSCs, TGF- β , iNOS, arginase, or Tregs which have been linked with T cell suppression⁵⁶ correlate with lower levels of effector T cell infiltrate post PD-1 blockade. If so, these may be surrogates for lack of efficacy with this strategy.

The local production of relevant cytokines and chemokines in serum and tumor tissue will also be examined using real-time PCR, western analysis, and commercially available RNase protection kits. The impact of the agent on the expression of potential immunosuppressive molecules such as indoleamine 2,3-dioxygenase, nitric oxide synthetase, and arginase in antigen presenting cells will also be evaluated. Post-treatment levels will also be characterized. For continuous immunologic endpoints, the following table shows the statistical power to be achieved for the detectable effect sizes (difference as a fraction of population standard deviation) within group comparisons of values and assuming either 100% or 80% of patients have paired samples (two-sided α =0.05).

Table 20: Statistical Power assessments for comparisons between two timepoints
within combination therapy (arm A)

	Statistical power (%) (bold)				
	Effect size within arms between two				
		ti	mepoint	ts	
Evaluable Sample size	0.6 0.7 0.75 0.8 0.9				
If 100% enrolled for analysis					
N=30	61 75 80 85 92			92	
If 80% enrolled for analysis					
N=24	52 65 71 76 85				

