13. STATISTICAL CONSIDERATIONS

13.1 Study Design/Endpoints

This is an open label phase 2 trial that randomizes 45 mCRPC patients (2:1 ratio) to radium-223 plus pembrolizumab combination therapy or to radium-223 monotherapy. The primary objective is to compare the increase in immune CD8+ and CD4+ T cell infiltration levels from baseline to 8 weeks on treatment between the two treatment arms.

Primary Endpoint:

Difference in tissue immune cell (e.g., CD4+/8+T) infiltration in the bone metastasis biopsy specimens from baseline to 8 weeks on treatments in both the combination and monotherapy arms.

Secondary Endpoints:

- Safety and Tolerability: grade 3 or higher adverse events that are considered treatment related according to NCI CTCAE (version 4.0)
- Progression-free survival (PFS): is defined as the time from the first dose of study drug to the earlier of the first documentation of definitive disease progression [as

defined by Response Evaluation Criteria in Solid Tumors (RECIST version 1.1) and PCWG2] or death due to any cause. Participants alive without disease progression are censored at date of last disease evaluation

• Overall survival as defined in 11.1.8

Exploratory Endpoints:

- Clinical-based endpoints
 - Changes in PSA
 - PSA response: defined as decline ≥50% from baseline to 12 weeks of therapy and which has been confirmed with a second PSA at ≥ 3 weeks later
 - Time to PSA progression as defined in 11.1.9
 - Time to normalization of alkaline phosphatase (if initially elevated)
 - Time to decrease in alkaline phosphatase (if initially elevated)
 - Symptomatic skeletal events (SSEs): Rate of SSEs and time to first SSE
 - Changes in osteoblastic activity on bone scan (assessed using the quantitative SPECT/CT)
 - Changes in quality of life, pain, and analgesic use, and time to introduction of analgesics
 - Immune-based endpoints
 - Quantify the CD8, CD4, and FoxP3+ CD4 (Treg) cell infiltration in the bone biopsy specimens, and to subsequently quantify the CD8/Treg and CD4/Treg ratios
 - Change in circulating T cell clonality
 - Induction of IgG antibody response
 - Changes in PD-L1 expression and co-regulation of other immune checkpoints such as TIM-3, LAG-3, and PD-L2
 - Changes in immunosuppressive cell populations and cytokines (e.g., MDSCs, Tregs, TGF-β, and iNOS)
 - Change in serum chemokines: (e.g., CXCL9, CXCL10)

- Changes in soluble PD-L1 ([name] Lab assay)
- Genomic-based endpoints

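### Antibody arrays (13.10): the own-median detection rule makes the number detected uninformative, and the between-arm count of 2- or 4-fold differences cannot separate induction from loss

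*Combined protocol and SAP*

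**What the plan says.** Section 13.1 lists "Induction of IgG antibody response" among the exploratory immune endpoints. Section 13.10 describes the analysis of the spotted antigen arrays in these steps.

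- Preprocessing and clustering: "After standard preprocessing of the protein array data", the data go to unsupervised clustering. The normalization is not described.
- Detection: "For each array, an antigen is identified as being detected if its value is above the median". The text does not say whose median is meant. No control spots, pooled reference or fixed value is named.
- Modulation: to find up- and down-modulated antibodies, "the difference in log2 intensity values of pretreatment and post-treatment samples will be taken for each patient".
- Between-arm comparison: "Number of antibodies with at least 2- or 4-fold difference between pretreatment and post-treatment samples will be compared between the treatment arms". The method named is the Wilcoxon rank-sum test, used two-sided.

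No alpha, power or expected count is given for this comparison. The text also does not say whether the detection call filters the fold-change count. The number of detected antigens is not itself named as an endpoint or compared between arms.

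**The concern.** There are two separate problems.

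First, a cutoff recomputed from each array as its own median fixes the share above it. The detection step is meant to find circulating antibody, but no background level enters it. It would call half the array detected in every untreated patient, and the number detected could not rise under treatment. Elsewhere the plan uses fixed cutoffs: 5% for PD-L1 positivity in Section 13.10, and 7.5% tumor purity in Section 13.11, where it is tied to a lower limit of accurate detection.

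Second, the endpoint is directional but the tested count is not. A patient with thirty rises and no falls scores the same as one with thirty falls and no rises. A significant arm difference could therefore come from loss of antibody, and a real difference in induction could be cancelled by an opposite difference in loss. The step before the test names both directions, but the comparison merges them.

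**Working it through.** The plan gives no figure to reproduce.

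**Inputs.** From the documents: the rules above, and 24 versus 12 evaluable patients (Section 13.4). Assumed, not from the documents: M = 500 antigens; log2 intensity SD 1.5 between antigens; measurement SD 0.3 at each time; alpha 0.05.

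**1. Share detected under the array's own median.** Without ties, the number of values above their own median is M/2 for even M and (M−1)/2 for odd M. For M = 500 that is 250, or 50.0%; for M = 101 it is 50/101 = 49.5%. Because the total is fixed, antigens newly detected must equal antigens newly undetected in every patient. Simulation gives 50.0% before and after in all four scenarios below. Which antigens are detected can change; how many cannot.

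**2. The planned fold-change count.** A log2 difference has noise SD 0.3 × √2 = 0.424. A 2-fold change means an absolute difference of at least 1.

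- An unchanged antigen crosses +1 with probability Φ(−1/0.424) = 0.0092, and crosses ±1 with probability 0.0184.
- An antigen truly up 4-fold (+2) crosses +1 with probability Φ(1/0.424) = 0.991.
- An antigen truly up 2-fold (+1) crosses +1 with probability 0.5.

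| Scenario | Expected count with at least 2-fold change |
|---|---|
| No response | 500 × 0.0184 = 9.2 |
| 20% up 4-fold | 100 × 0.991 + 400 × 0.0184 = 106.5 |
| 40% up 4-fold | 200 × 0.991 + 300 × 0.0184 = 203.7 |
| All up 2-fold | 500 × 0.5 = 250 |

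Simulation agrees to within about one antigen. If the median call is also used as a filter (detected before or after), the counts are about 6, 90, 159 and 136. The compared count responds either way.

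**3. Direction.** Let a share u of antigens rise 4-fold and a share v fall 4-fold.

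Expected rises = 500 × [0.991u + 0.0092(1−u−v)]; for falls, exchange u and v.

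- Arm A, u = 3%, v = 1%: rises 14.9 + 4.4 = 19.3; falls 5.0 + 4.4 = 9.4; total 28.7.
- Arm B, u = 1%, v = 3%: rises 9.4; falls 19.3; total 28.7.

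The totals are equal for any symmetric noise, because exchanging u and v leaves a two-way count unchanged. At 24 versus 12 the two-sided rank-sum test rejects in about 5% of simulated runs on the two-way count and in 100% on rises alone.

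Now let the arms differ only in losses: Arm A u = 1%, v = 3%; Arm B u = v = 1%.

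- Arm A: rises 9.4, total 28.7.
- Arm B: rises 5.0 + 4.5 = 9.5, total 19.0 (twice 9.5).

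The two-way test rejects in 98% of runs or more. The test on rises stays close to the nominal 5%.

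**4. Normalization.** If each array is centred on its own median, a rise shared by all antigens is subtracted out, and the all-up-2-fold count falls from 250 to the no-response level of about 9. The plan does not say that its preprocessing does this.

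**The case against.** A reader might infer from the detection rule that an induced antibody response cannot change the result at all. The documents do not support that. The quantity compared between arms is the number of antibodies with a 2- or 4-fold change in log2 intensity, which the detection call does not determine, and the working shows that it responds strongly. The fixed 50% describes a statistic that the plan never says it will test.

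It can also be said that the plan does not state whose median is used, and that detected need not mean seropositive. Both are fair. The array's own median is the natural reading of a rule stated for each array, but it remains a reading, and the first part of this point depends on it.

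On direction, the plan names up- and down-modulated antibodies and the log2 difference is signed, so the analyst can separate them. When a response is nearly all upward, pooling changes little: with 20% of antigens up 4-fold, about 103 of the 106 or 107 counted are rises. What stands is that the one between-arm test stated for this endpoint is not split by direction, and this matters when losses differ between arms.

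Finally, this is one of several exploratory endpoints, with no decision rule attached. That limits the severity but does not remove the ambiguity.

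**Conclusion.** The point holds in two limited parts.

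- If the median is the array's own, the number detected is about 50% in every sample and carries no information on presence or induction of antibody. The role of the call in the later count is also undefined.
- Whatever median is meant, the between-arm test counts differences either way and so cannot tell induction from loss. Opposite patterns in the two arms can give the same expected count, and a difference in losses alone can produce a significant result.

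The fold-change analysis as a whole is not blind to a response. The rejection rates rest on the assumed antigen number, noise and response shares. The 50% identity and the symmetry of the two-way count do not. Severity is low: the endpoint is exploratory and the primary analysis in Section 13.7 is unaffected.

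**What to change.** In Section 13.10:

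- Compare between arms the number of antigens that rise at least 2-fold, and likewise at least 4-fold. Report falls as a separate count.
- Replace the per-array median with one background-based cutoff applied unchanged to all arrays, for example from negative-control spots if the arrays carry them (the documents do not say), or drop the detection call.
- If a detection call is kept, state what it is used for. Do not make a high-percentile cutoff a condition of the induction count. The 95th percentile of pooled baseline arrays would fix the baseline share at 5% by construction. Required together with a 2-fold rise, it would keep only about 37 of 103 antigens in the 20% scenario.
- Name the normalization.

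The cost is a few sentences and slight recoding, with no new samples. The downside is that a fixed cutoff needs between-array normalization, and this must not centre each array on its own median, or a shared rise is removed.

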13.7 Analysis of Primary Endpoints

The extent of immune cell infiltration (in the bone biopsy specimens): The comparison of an increase in CD4+ T or CD8+ T cell infiltration levels measured in the bone biopsy specimen from baseline and 8 weeks between the treatment arms will use Wilcoxon rank sum tests. The difference and the 95% confidence interval will also be provided.

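### No supplied text masks the readers of the primary CD4+/CD8+ biopsy endpoint to treatment arm in this open-label trial

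*Combined protocol and SAP*

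**What the plan says.** Section 13.1 opens with "This is an open label phase 2 trial that randomizes 45 mCRPC patients" in a 2:1 ratio, and gives the primary endpoint as "Difference in tissue immune cell (e.g., CD4+/8+T) infiltration in the bone metastasis biopsy specimens from baseline to 8 weeks on treatments" in both arms. Section 13.7 specifies the test: the increase in CD4+ or CD8+ infiltration "measured in the bone biopsy specimen from baseline and 8 weeks between the treatment arms will use Wilcoxon rank sum tests". It says nothing about how the slides are read.

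The measurement itself is described only in section 13.10: "IHC will be performed on bone metastasis biopsies obtained at baseline and on treatment to quantify tumor infiltration by CD8+ T cells", together with Tregs and total CD4 cells, in normal and in tumor tissue. It gives no reader, number of readers, counting method or masking.

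The one reader-masking statement comes later in the same section and concerns PD-L1. The sentence "Tumor tissue from each patient's biopsy will be evaluated by IHC for PD-L1 levels prior to administration of the drug" fixes the time point. The next adds "Two independent pathologists who are blinded to the patients' clinical outcomes (e.g., response, survival) will score the percentage of tumor cells" with cell-surface staining. Treatment arm and the CD4/CD8 stains are not mentioned.

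Section 9.1 sends the reader to the statistical section for endpoints and to the laboratory manual for collection, processing and shipping. Section 9.1.1 ends with a general reference to that manual, which is not among the supplied documents. Section 9.1.1 also allows a first biopsy to be judged, after enrollment, not useful for the primary endpoint, in which case the on-treatment biopsy is not required. Section 13.6 limits the primary analysis population to patients with both biopsies, and section 13.2 replaces patients if more than 9 have inadequate specimens.

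**The concern.** In an open-label trial, masked reading of the endpoint is what keeps knowledge of treatment out of the measurement. The plan specifies two independent, masked readers for an exploratory marker and nothing comparable for the primary endpoint.

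If whoever selects regions, counts cells or sets up automated counting knows the arm, the recorded increase can differ between arms for reasons unrelated to treatment. Randomization does not protect against an error made at the reading stage, and a rank test treats an arm-specific shift as a treatment effect. A positive primary result would then be open to the criticism that reading explains it.

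The adequacy judgment in section 9.1.1 raises the same issue. It affects who enters the paired analysis and who counts toward replacement, and no section says that it is made without knowledge of arm when it falls after randomization.

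**Working it through.** **1. Side by side**

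| | PD-L1 read (13.10) | CD4/CD8 read (13.7, 13.10) |
|---|---|---|
| Role | Exploratory | Primary |
| Tissue | Pre-drug | Baseline and week 8 |
| Readers stated | Two independent pathologists | None stated |
| Masked to clinical outcome | Yes | Not stated |
| Masked to arm | Not stated | Not stated |

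No other section fills the right-hand column. Section 11.1.3 calls the imaging reviewers independent but does not say they are blinded. The only other mention of blinding, in section 2.2.1, describes the earlier phase 3 radium-223 trial.

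**2. The plan's own figure.** Inputs from section 13.4: 24 and 12 evaluable patients, two-sided alpha 0.05, difference 70%, SD 58%.

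- Effect size: 0.70/0.58 = 1.207, stated as 1.2.
- Normal approximation with the Wilcoxon efficiency 3/π: k = √[(24 × 12/36) × 3/π] = √(8 × 0.955) = 2.764.
- Power ≈ Φ(1.2 × 2.764 − 1.960) = Φ(1.357) = 91.3%, against the stated 91%.
- The same formula gives 60, 70, 79 and 86% for effect sizes 0.8 to 1.1, against 59, 69, 78 and 85% in Table 18. Direct simulation with normal data gives 89.0% at 1.2.

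The power statement reproduces and is not in dispute.

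**3. What an arm-specific reading shift would do.** Assume no true difference, and let reading add b SDs to the Arm A increase only. The documents give no figure for b, so a range is shown. The false-positive rate is approximately Φ(bk − 1.960) + Φ(−bk − 1.960).

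| Assumed shift b | Percentage points at SD 58% | Formula | Simulated Wilcoxon |
|---|---|---|---|
| 0 | 0 | 5.0% | 4.9% |
| 0.1 | 5.8 | 5.9% | 5.6% |
| 0.25 | 14.5 | 10.6% | about 10% |
| 0.5 | 29 | 28.2% | 26% |

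Worked line for b = 0.25: bk = 0.691; Φ(−1.269) + Φ(−2.651) = 0.102 + 0.004 = 10.6%. The simulations use normal data and 24 versus 12 patients. The 0, 0.1 and 0.5 rows come from 100,000 trials each. At 0.25, runs of 20,000 and 40,000 trials gave 9.8% and 10.1%.

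**4. What an equal shift would do.** If reading adds the same amount c to the increase in both arms, each comparison of an Arm A patient with an Arm B patient is between X + c and Y + c. The ordering, and so the rank sum statistic, does not change. Knowing the time point but not the arm therefore does not produce the rates above. It matters mainly for the within-arm comparisons between time points, such as those powered for Arm A in Table 20.

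**5. Can arm be masked?** Section 9.1.1 embeds the tissue in paraffin, which allows coded, batched reading. Tables 3 and 4 give both arms radium-223 every 4 weeks for the first three doses, and the biopsy is set at about week 8, so planned radium exposure does not by itself reveal the arm.

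**The case against.** The strongest reply is that this is silence, not a stated unmasked read. No section says that slides carry the arm assignment. The laboratory manual has not been seen, and although section 9.1 limits its role to collection, processing and shipping, the reference in section 9.1.1 is open-ended. Counting may be automated, which would reduce the scope for expectation. All of this stands, and it limits the point to what the supplied text permits. It does not remove it: a safeguard for the primary endpoint belongs in the plan, and automated counting may still need someone to choose regions and settings.

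Four stronger readings are tempting, and the documents do not support them:

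- **That the PD-L1 rule masks the wrong thing.** For a pre-drug marker later related to outcome, masking to response and survival is appropriate. Section 13.1 also lists changes in PD-L1, so later reads are possible, but the sentence makes no claim about the primary endpoint. The gap is in 13.7 and in the CD4/CD8 text of 13.10.
- **That the reading laboratories hold an expectation, or that a pathologist outlines tumor by hand.** Section 13.10 states the protocol's hypothesis that counts will rise. It does not attribute that to the readers, does not say which site reads the IHC and describes no region-selection step.
- **That knowing the time point alone biases the primary test.** An equal shift in both arms cancels.
- **That the false-positive rates estimate what will happen in this trial.** They follow from assumed shifts. At 0.1 SD the effect is slight, and 0.5 SD means 29 percentage points of misreading confined to one arm.

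**Conclusion.** The point holds as a gap in the protection of the primary comparison. The trial is open label, the primary endpoint is read from tissue, and no supplied text masks the CD4/CD8 readers to arm. A team could follow the plan exactly and read the slides with the arm known.

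Only reading that differs by arm biases the primary Wilcoxon test. The size of any such bias is unknown. For assumed shifts of 0.1 to 0.5 SD the two-sided false-positive rate would be about 5.6% to 26% instead of about 5%, given normal data, 24 versus 12 patients and no true difference. The conclusion also assumes that no masking rule exists in the unseen laboratory manual. If one does, the remaining task is to move it into the plan.

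**What to change.** Add the following to sections 13.7 and 13.10:

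- CD4/CD8 slides carry a random code, with the key held by the statistician.
- Each patient's baseline and week-8 slides are read in the same batch, in mixed order.
- Whoever selects regions, counts cells or sets up automated counting is masked to arm, and to time point where feasible, until the primary data are locked. Archival baseline tissue, which the protocol allows, may make time-point masking imperfect.
- The same masking applies to whoever judges a biopsy adequate for the primary endpoint, where that is decided after randomization.
- The counting method, the number of readers and the handling of disagreements are stated.

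The cost is slide coding and waiting to read in batches. The plan contains no interim look at the IHC (the early review in section 13.5 is for safety), so the wait delays no planned analysis. Sample size, alpha, power, the number of biopsies and patient procedures stay the same.

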Blocking antibodies, such as pembrolizumab have been developed to counteract this tumor evasion mechanism. Pembrolizumab is a potent and highly selective humanized monoclonal antibody (mAb) of the IgG4/kappa isotype designed to directly block the interaction between PD-1 and its ligands, PD-L1 and PD-L2. KeytrudaTM (pembrolizumab) has recently been approved in the United Stated for the treatment of patients with unresectable or metastatic melanoma and disease progression following ipilumumab and, if BRAF V600 mutation positive, a BRAF inhibitor.

In a phase 1 study of multiple solid tumors, pembrolizumab has demonstrated tolerability and preliminary efficacy. The most frequent AEs were fatigue, asthenia, fever, chills, myalgias, diarrhea, rash, and pruritus.^{19,20} While PD-L1 has not been shown to be upregulated in the majority of prostate cancer cases sampled,²¹ data from work with other PD-1 pathway blocking antibodies such as Genentech's anti-PD-L1 molecule MDPL3280A demonstrate that the PD-L1 expression on the tumor infiltrating immune cells is also of importance and correlates with a higher chance of response to the drug.

Preclinical and Clinical Trial Data:

Refer to the Investigator's Brochure for Preclinical and Clinical data for full details.⁵

Clinical Summary of Results

As of 18-Oct-2013, 1,000 patients have been treated with MK-3475 at several dose-schedules, including 10 mg/kg every 2 weeks. MK-3475 has been generally well tolerated, as expected based on preclinical findings and other anti-PD-1 monoclonal antibodies. As of 18-Oct-2013 no serious infusions reactions have been reported in PN001. Less than 1% of patients thus far assayed had confirmed positive ADA samples and among these, no or no clear impact on exposure has been observed. There is no contraindication to further clinical investigation with MK-3475.

Pharmacokinetics were as expected, based on MK-3475 being an IgG mAb and based on preclinical data, which support dosing once every 2 or 3 weeks.

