Biopsies will be performed by an interventional radiologist under CT or PET-CT guidance. Blood samples will be drawn within 30 days of the biopsy to document an acceptable coagulation profile (INR < 1.5, PTT < 45, platelets >50,000). Aspirin and/or Plavix should be discontinued 5 days prior to the biopsy. On the day of the biopsy, a short physical exam will be performed by the radiologist including assessing the patient's general ASA score and airway rating. Informed written consent will be obtained following discussion of the risks (bleeding, infection, adjacent tissue injury, and pain) and benefits of the procedure. Biopsies will be performed using standard coaxial techniques under CT guidance without the administration of intravenous contrast. Several bone specimens (when possible, ideally at least 4-6 cores) will be obtained. Samples will be given to a dedicated technician present during the procedure for sample processing. Conscious sedation will be administered by a trained radiology nurse using small doses of Versed and fentanyl titrated to the patient's level of discomfort. Following the biopsy, patients will be observed for 2 hours following their last dose of conscious sedation for any complications (severe pain, hematoma, neurologic deficit) prior to departing with a chaperone.

See Laboratory Manual for further details.

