L: Diagnostic CT chest and CT or MRI of the abdomen and pelvis and bone scan including SPECT/CT should be obtained at baseline and every 12 weeks (+/- 7 days). (NOTE: SPECT/CT will be done only at DFCI.) Scans should remain on an every 12 week schedule (+/- 7 days) even if dose delays occur.

M*: Correlative immune studies: will be obtained and transported overnight at room temperature to the [name] Lab at UCSF. Samples for immune studies will be done at week 1 (pre-dose), week 5, week 9, week 13, week 21 and at the time of progression for those patients still on study.

N: Bone biopsy: archival tissue is permitted for baseline analysis. IR guided bone biopsy will be done at week 8 (+3 weeks) after the second dose of radium-223. If the second dose cannot be given for safety reasons, biopsy should still be performed within the window detailed here.

O: Blood samples for cell free DNA (cf-DNA) will be performed at treatment initiation (week 1, pre-dose), on treatment (week 5 and 13), and at time of progression.

P: Quality of life, pain and analgesic use will be measured via the FACT-P (Appendix B), Brief Pain Inventory (Short Form) (Appendix C), and analgesic diary (Appendix D) prior to treatment, at week 5, 9, then every 6-8 weeks after week 9 (as schedules differ between the two arms), and at treatment progression/off study visit.

Q: After progression/treatment discontinuation, follow the participant for survival, receipt of next line therapies, and post-treatment SSEs every 6 months until death or 2 years after treatment discontinuation.

R: Arm A study assessments will continue based on the same schedule as detailed for weeks 1-13 when pembrolizumab is given alone (e.g., visits, labs, assessments every 3 weeks only). If radium-223 is resumed upon progression, assessment schedule and radium-223 + pembrolizumab dosing will resume based on the schedule detailed for weeks 1-13. Arm B study assessments and radium-223 dosing will continue based on the same schedule detailed for weeks 1-13 up to 6 doses without breaks except for toxicity/intolerance (Section 6.2).

Note: For both arms: Immune studies will follow the schedule detailed in footnote M*

S: End of Treatment visit should occur within 30 days after last study treatment.

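### The any-core 5% rule makes PD-L1 positivity depend on how many cores are read, and the PD-L1 method names only a pre-drug time point although the endpoint is a change

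*Combined protocol and SAP*

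**What the plan says.** Section 13.10 has two pathologists who "will score the percentage of tumor cells exhibiting cell-surface staining for PD-L1". It then states that "PD-L1 positivity is defined per core by a 5% expression threshold", and that a patient with several cores counts as "positive if any specimen meets this criterion". Other cut-offs are to be explored but are not named.

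The number of cores is an aim and not a requirement. Section 9.1.1 says "Several bone specimens (when possible, ideally at least 4-6 cores) will be obtained" and allows core needle or excisional biopsy. Footnote N of the study calendar (Section 10) adds that "archival tissue is permitted for baseline analysis".

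On timing, the exploratory immune endpoints in Section 13.1 include "Changes in PD-L1 expression and co-regulation of other immune checkpoints", with TIM-3, LAG-3 and PD-L2 given as examples. Section 13.10 says that each patient's tumor tissue "will be evaluated by IHC for PD-L1 levels prior to administration of the drug" and that the other checkpoints are stained similarly. Two paragraphs later, after the text on cytokines and immunosuppressive molecules, one sentence says that post-treatment levels will be characterized as well. It does not name PD-L1.

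**The concern.** A rule that takes the best of several cores gives each further core another chance to cross the threshold. Two patients with the same expression can be classified differently because one had two cores read and the other six. The plan sets no minimum number of tumor cells per core for staining (the 20% tumor-nuclei requirement in Section 9.5 is for DNA isolation), so a small core with a few stained cells can decide the patient's status.

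If the same rule is applied at week 8, the risk becomes a spurious change. An archival baseline sample with few cores, followed by an on-treatment biopsy that aims for four to six, would tend to show a rise in PD-L1 positivity with no biological change. That is the direction of the adaptive upregulation proposed in Section 2.3.

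The timing gap is separate. A change needs two measurements, and the PD-L1 method names one.

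**Working it through.** The plan gives no PD-L1 positivity rate, core-count adjustment or PD-L1-specific power, so there is no stated figure to reproduce. Table 20 covers continuous paired measures and not this classification.

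**Inputs from the documents:** threshold 5% per core and any-core patient rule (13.10); core count k not fixed, ideally at least 4-6 (9.1.1); archival baseline allowed (Section 10, footnote N).

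**Inputs assumed:** the share p of cores reaching 5%, the within-patient correlation between cores (ICC), the true PD-L1-positive fraction f, and tumor cells per core m. None is in the documents, so ranges are shown.

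**Check 1: cores differ in status, with 10% of cores positive overall.**
- Independent cores: P(positive) = 1 − (1 − p)^k. With p = 0.10 and k = 6, 1 − 0.9^6 = 46.9%.
- Correlated cores (beta-binomial): with M = (1 − ICC)/ICC, a = pM and b = (1 − p)M, P(positive) = 1 − product over j = 0 to k−1 of (b + j)/(a + b + j). At ICC 0.5, a = 0.1 and b = 0.9, so for k = 2 this is 1 − (0.9/1)(1.9/2) = 14.5%.

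| ICC | 1 core | 2 cores | 4 cores | 6 cores |
|---|---|---|---|---|
| 0 | 10.0% | 19.0% | 34.4% | 46.9% |
| 0.3 | 10.0% | 16.3% | 24.3% | 29.4% |
| 0.5 | 10.0% | 14.5% | 19.4% | 22.3% |
| 0.9 | 10.0% | 10.9% | 11.7% | 12.1% |

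**Check 2: expression is uniform and below 5%, so a positive call is counting noise.** The per-core probability is q = P(X ≥ 0.05m), rounding the cut up to a whole cell, with X binomial(m, f). The patient probability is 1 − (1 − q)^k. For m = 100 and f = 2%, q = P(X ≥ 5) = 5.08%, and six cores give 1 − 0.9492^6 = 26.9%.

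| True fraction | Cells per core | 1 core | 6 cores |
|---|---|---|---|
| 1% | 100 | 0.3% | 2.0% |
| 2% | 100 | 5.1% | 26.9% |
| 3% | 100 | 18.2% | 70.1% |
| 2% | 50 | 7.8% | 38.7% |
| 2% | 200 | 0.7% | 4.4% |

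**Check 3: would a 5% cut on the pooled percentage remove the problem?** Not fully. With m = 50 and f = 2%, two pooled cores give P(X ≥ 5 of 100) = 5.1%, and six give P(X ≥ 15 of 300) = 0.1%. At f = 3% the figures are 18% and 4%. A pooled cut still depends on core count, now in the opposite direction. The continuous pooled percentage does not have this bias: under the same model its expected value is f for any k, and only its precision changes.

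**Check 4: timing, by comparing text.** Section 13.10 names two time points for T-cell staining, for T-cell receptor sequencing and for antibody arrays. For PD-L1 it names one, before drug. The endpoint in 13.1 needs two.

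**The case against.** The strongest reply has five parts.

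- *The plan never applies the any-core status at week 8, and the endpoint is change in expression, not in status.* This stands. The spurious-change risk is conditional on the rule being carried forward. Because a percentage is scored, a continuous analysis is already possible; the plan only needs to choose it.
- *No analysis uses PD-L1 status.* This also stands. No test, power statement or treatment decision depends on it, and nothing in the documents suggests that baseline core number would favor an arm.
- *Change can be measured.* A reader might infer from the pre-drug wording that the stated change cannot be measured at all. The documents do not support that. Paired biopsies are scheduled, and the sentence on post-treatment levels may be meant to include PD-L1. The text is under-specified.
- *Tumor cells are a proper compartment.* A reader might infer that scoring tumor cells alone defeats the rationale. Section 2.3 proposes upregulation by the tumor itself, which tumor-cell scoring at both times would capture. Section 2.2.2 does say that "PD-L1 expression on the tumor infiltrating immune cells is also of importance and correlates with a higher chance of response to the drug", so an immune-cell score would be a useful addition, but its absence does not prevent measurement of change.
- *Pooling has its own cost.* It dilutes a small focal positive area that the any-core rule would catch. This is true and is a reason to keep the any-core result as description.

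Exploring other cut-offs is not an answer: it moves the threshold and leaves the dependence on core count in place.

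**Conclusion.** The point holds as a low-cost improvement to one exploratory endpoint. Under the rule as written, patient positivity increases with the number of cores for any per-core rate strictly between 0 and 1, unless cores within a patient agree perfectly. The size cannot be fixed from the documents. From 2 to 6 cores, with 10% of cores positive, it ranges from about 1 percentage point (ICC 0.9) to about 28 points (independent cores). From 1 to 6 cores of 100 cells, it ranges from about 2 points at a true fraction of 1% to about 52 points at 3%. No single figure in these ranges should be read as the expected effect.

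The mismatch between a change endpoint and a pre-drug staining time point is a gap in wording that should be closed. The laboratory manual, which was not available, may settle core handling or timing; the protocol and its statistical section do not. The CD4/CD8 primary comparison and the sample size are unaffected.

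**What to change.** In Section 13.10:

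1. For the change endpoint, define PD-L1 at each biopsy as PD-L1-positive tumor cells divided by all tumor cells, summed over every evaluable core, and analyze it as a continuous percentage.
2. State that PD-L1, PD-L2, TIM-3 and LAG-3 are scored on both the baseline and the week-8 specimen.
3. Analyze the change with the Wilcoxon tests that Section 13.9 already uses: signed-rank within the combination arm and rank sum between arms.
4. Record the number of cores and of tumor cells read at each biopsy, and whether baseline tissue was archival.
5. Keep the any-core 5% status as a descriptive line reported with core count. Do not replace it with a 5% cut on the pooled value, which also depends on core count.
6. Optionally, have the same pathologists record PD-L1 on immune cells on the same slides.

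The cost is a change of wording and somewhat more reading time on tissue that is already collected. The downside is that a pooled percentage dilutes small focal positivity, which the descriptive line preserves.
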